Gasselhuber, et al. (2012) published a computational model of doxorubicin concentration in liver tumor tissue following combination therapy with ThermoDox and mild hyperthermia, (target temperature 43°C). Their model found a direct correlation between duration of hyperthermia and doxorubicin tumor tissue concentration. This finding suggests the hypothesis that, when used with ThermoDox, length of heating time can be used to ensure delivery of a doxorubicin dose needed to provide a therapeutic effect in tumor tissue. Although this study utilized mild hyperthermia, the principle of heat time translating into doxorubicin dose is readily applicable to RFA procedures.

A 2013 study in healthy pigs receiving intravenous ThermoDox and RFA of the liver is consistent with the hypothesis that doxorubicin target tissue concentration directly covaries with duration of hyperthermia (Swenson, 2014). Furthermore, fluorescence imaging found high doxorubicin concentrations in the margin of the ablation zone and in areas where ablations overlapped, supporting the hypothesis that ThermoDox addresses any microscopic tumors left behind in the clefts of overlapping ablations.

Haemmerich and Rossmann (2013) conducted a ThermoDox + RFA modeling study. They found that the amount of bioavailable doxorubicin in the tumor margin increases as the actual heating time increases. They also found that beginning RFA 15 minutes after starting a 30-minute ThermoDox infusion maximizes the amount of bioavailable doxorubicin in the tumor margin compared to beginning RFA later.

In Celsion's initial phase III trial, the HEAT Study (Protocol 104-06-301), the criterion for RFA adequacy was that it ablate each target lesion plus a 360° 1-cm tumor margin; there was no attempt to manage RFA so as to also increase doxorubicin tumor tissue concentration. The results of the HEAT Study became available in 2013. The trial achieved the expected level of safety. The overall safety profile was consistent with literature reports for liposomal doxorubicin and free doxorubicin commercial labels. Other than reversible neutropenia and leukopenia, both treatment-related adverse events \geq grade 3 and serious adverse events were rare, affecting < 5% of patients in either arm. However, the primary endpoint of progression free survival (PFS) was not met. Patients are still being followed for overall survival (OS).

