6.2.3 Exclusion Criteria

Subjects meeting any of the following criteria will be excluded from the study:

1. Is scheduled for liver transplantation.
2. Expected ablation volume $>$ 30% of total liver volume or removal of 3 hepatic segments
3. More than 1 lesion identified during baseline.
4. Have previously received therapeutic treatment for HCC outside the study protocol or is expected to receive concomitant HCC treatment prior to PFS event.
5. Have serious medical illnesses including, but not limited to, congestive heart failure, myocardial infarction or cerebral vascular accident within the last six months, or life threatening cardiac arrhythmias.
6. Have previously received any anthracycline outside the protocol.
7. Have extrahepatic metastasis.
8. Have portal or hepatic vein tumor invasion/thrombosis.
9. Have body temperature $>$ 101°F (38.3°C) immediately prior to study treatment.
10. Baseline laboratories (repeat lab tests are permitted to evaluate eligibility during the Screening Period. Lab results must be within protocol range prior to study treatment.)
 - Absolute neutrophil count $<$ 1500/mm³
 - Platelet count $<$ 75,000/mm³
 - Hgb $<$ 10.0 g/dL (unless the hemoglobin value has been stable, the subject is cardiovascularly stable, asymptomatic and judged able to withstand the RFA procedure)

Note: If clinically indicated, subjects may receive platelets or packed RBC transfusions and be re-evaluated after condition is treated.

11. Baseline Chemistry
 - Serum creatinine \geq 2.5 mg/dL or calculated creatinine clearance (CrCl) \leq 25.0 mL/min.
 - Serum bilirubin $>$ 3.0 mg/dL.
 - Serum albumin $<$ 2.8 g/dL.
12. Have any known allergic reactions to any of the drugs or liposomal components or intravenous imaging agents that prohibit the ability to complete the imaging requirements.
13. Are pregnant or breast-feeding. In women of childbearing potential, a negative serum pregnancy test is required prior to study treatment.
14. Women of childbearing potential and men who are not practicing an acceptable form of birth control (i.e. diaphragm, cervical cap, condom, surgical sterility or birth control pills. Women whose partner has or men who have undergone a vasectomy must use a second form of birth control).

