6.2.4 Potential Risks and Benefits

Potential Risks

There are risks to subjects participating in this study. As reviewed in Sections 3.2 and 8.4, there are risks associated with the RFA procedure. There are also risks associated with the use of doxorubicin HCl. Based on the clinical experience to date, there does not appear to be a substantial unique risk for ThermoDox, but unexpected AEs could occur. The RFA procedure itself has a relatively low major complication rate. The safety profile of RFA is provided in Sections 3.2 and 8.4. Doxorubicin HCl, the active agent in ThermoDox, is routinely given in chemotherapy regimens for multiple cycles after appropriate recovery intervals, usually at least 3 weeks. In contrast, the vast majority (84.8%; 291/343) of subjects in the RFA plus ThermoDox arm in the prior trial received only a single dose of 50 mg/m² of ThermoDox.

The primary toxicities of doxorubicin are myelosuppression and cumulative-dose cardio-toxicity. The risk of developing impaired ventricular ejection fraction (LVEF) is generally proportional to the cumulative exposure. The probability of developing cardiomyopathy is estimated to be 1 to 2% at total cumulative dose of 300 mg/m² of doxorubicin HCl. (Pfizer Doxorubicin HCL Prescribing Information). The clinical safety profile of ThermoDox as observed to date is consistent with the known safety profile of doxorubicin HCl. Subjects in this study must have reasonable marrow reserve and adequate cardiac function. Subjects with prior doxorubicin exposure are excluded from this study (except in the case of completion of treatment or re-treatment). Expected non-hematological toxicities include cardio-toxicity, neuropathy, volume retention, hypersensitivity, mucositis, GI disturbances, nausea, and vomiting. Local toxicity in the liver will be carefully evaluated. Renal function will be closely monitored with urinalysis. BUN/Urea and creatinine will be monitored as nephrotoxicity has been seen in previous animal studies.

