10.1.12 Laboratory Analytes

Table 2: Laboratory Analytes

Hematology	Clinical Chemistry		Urinalysis
Hematocrit	Sodium	AST/SGOT	pH
Hemoglobin	Potassium	ALT/SGPT	specific gravity
RBC count	Chloride	Alkaline Phosphatase	Protein
WBC count	Glucose	Total protein	Glucose
Differential WBC count	Urea nitrogen	Albumin	Ketones
Platelets	Creatinine	Calcium	Blood
PT	Total bilirubin	AFP	WBC/HPF
INR			RBC/HPF
			Crystals

The laboratory will perform evaluations of the analytes listed in Table 2 above. Evaluations should take place as follows:

- Within 21 days prior to study drug infusion- Repeat laboratory analysis is permitted to evaluate eligibility prior to treatment. The repeat analysis results must meet the eligibility criteria prior to study drug infusion.
- Day 14 (+/- 3 days)
- Day 28 (+/- 3 days)
- Day 7 (+/- 3 days) for subjects with elevated bilirubin

Additional hematologic tests (CBC with differential) will be collected at months 5, 9, and 13 or disease progression, whichever occurs first.

Additional post-treatment liver function tests (Chemistry and PT/INR), will be collected at months 5, 9, 13, 17, 21, and 25 (+/- 2 weeks) or disease progression, whichever occurs first.

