6.4.2 Laboratory Parameters

Hematological and chemistry laboratory parameters will be graded according to the NCI CTCAE v.4.03 criteria (see appendix), where applicable. Absolute values and changes from baseline will be summarized by treatment arm at each visit. Shift tables will be provided for the shift from Baseline to the highest post Baseline value. The last on-study value will also be presented (called 'End of Study'), with change from baseline. In addition, worst severity grade, time to event, and time to resolution will also be summarized.

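### As worded, SAP 6.4.2 builds every laboratory shift table on the highest post-baseline value, which hides falls, including reversible leukopenia and neutropenia

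*SAP*

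**What the plan says.** SAP 6.4.2 (Laboratory Parameters) covers hematology and chemistry together: "Hematological and chemistry laboratory parameters will be graded according to the NCI CTCAE v.4.03 criteria (see appendix), where applicable". It then lists the outputs:

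- By visit: "Absolute values and changes from baseline will be summarized by treatment arm at each visit".
- Shift tables: "Shift tables will be provided for the shift from Baseline to the highest post Baseline value".
- Further summaries: "In addition, worst severity grade, time to event, and time to resolution will also be summarized".

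The shift rule names no test, no direction and no exception. No shift to the lowest value or to the worst grade is planned. The list of tables is kept in a separate document (SAP 8).

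The protocol says where a laboratory signal is expected. Section 6.2.4 states: "The primary toxicities of doxorubicin are myelosuppression and cumulative-dose cardio-toxicity". Section 3.3 singles out two cytopenias when it reports the prior phase III trial: "Other than reversible neutropenia and leukopenia, both treatment-related adverse events" of grade 3 or above, and serious events, are described there as rare.

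**The concern.** A safety shift table cross-classifies each subject's baseline category against the worst category reached on study. It separates a new or worsened abnormality from one already present at entry. That only works if the post-baseline value is the worst one for that test, and for a test graded on low values the worst value is the minimum.

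Using the maximum throughout means that one recovered sample is enough to remove a fall from the table. Recovery is what the protocol leads one to expect: it calls the earlier neutropenia and leukopenia reversible, and Protocol 11 permits transfusions and colony-stimulating factors for myelosuppression.

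Safety is a secondary objective, and SAP 6.4 puts laboratory assessments alongside adverse events as its main focus. At stake are shift tables that understate the toxicity most expected of the drug and disagree with the worst-grade summary planned in the same paragraph.

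**Working it through.** The plan states no figure for the shift tables, so there is none to reproduce. The check sets the rule against the SAP's own grading table.

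**1. Direction of grading.** Inputs: tests collected in Protocol Table 2 (10.1.12) that also have a row in SAP Table 10.2.1. Neutrophils and lymphocytes come from the differential count. Collected tests without a grading row, such as hematocrit and chloride, are left out.

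| Graded in SAP Table 10.2.1 | Tests | Number | Effect of taking the highest value |
|---|---|---|---|
| Low only | neutrophils, platelets, albumin | 3 | wrong direction |
| Low and high | WBC, lymphocytes, hemoglobin, sodium, potassium, calcium, glucose | 7 | low direction lost |
| High only | bilirubin, ALT, AST, alkaline phosphatase, creatinine, PT, INR | 7 | correct |

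Total: 3 + 7 + 7 = 17. Low direction lost: 3 + 7 = 10 of 17.

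**2. When a fall would appear.** Let c be the upper cut-off of a low-direction grade and x1, ..., xk the post-baseline values. The highest value is below c only if every xi is below c. A subject without progression has k = 5 scheduled blood counts: Days 14 and 28, and then "Additional hematologic tests (CBC with differential) will be collected at months 5, 9, and 13 or disease progression, whichever occurs first". Subjects with elevated baseline bilirubin have a sixth at Day 7. A Grade 3 or 4 neutrophil or platelet count therefore enters the table only if all available counts are that low.

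**3. Worked examples.** The values are assumed and show direction only. Cut-offs are from SAP Table 10.2.1; the lower limits of normal (neutrophils 2.0, WBC 3.5, in 10³/µL) are from SAP Table 10.1.1.

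| Test | Baseline | Post-baseline values | Shift by highest value | Shift by lowest value |
|---|---|---|---|---|
| Neutrophils | 3.5 | 0.4, 3.0, 3.4, 3.6, 3.5 | Grade 0 to 0 | Grade 0 to 4 |
| WBC | 5.5 | 0.9, 4.8, 5.4, 5.6, 5.5 | Grade 0 to 0 | Grade 0 to 4 |
| WBC | 2.8 | 1.4, 2.9, 3.6, 3.5, 3.6 | Grade 2 to 0 | Grade 2 to 3 |

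In the last row the planned table reports improvement for a subject who worsened. The worst-grade summary would report the same subject as Grade 3.

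**4. Can the worst-grade summary stand in?** It can where entry limits keep the baseline at Grade 0 or 1, because any worst Grade 2 to 4 is then a worsening. Protocol 6.2.3 requires neutrophils of at least 1.5 and platelets of at least 75 (10³/µL), both Grade 1 or better, so those two tests are settled. The other 10 − 2 = 8 are not:

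- WBC and lymphocytes have no entry limit of their own. WBC cannot be below the neutrophil count, so the limit implies only WBC of at least 1.5, which allows baseline Grades 0 to 3.
- Albumin of 2.8 to below 3.0 g/dL is eligible and already Grade 2.
- Hemoglobin below 10 g/dL excludes a subject "unless the hemoglobin value has been stable, the subject is cardiovascularly stable" and meets the remaining conditions, so Grade 2 or worse at entry is possible.
- Sodium, potassium, calcium and glucose have no entry limit.

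**The case against.** The strongest reply is that the sentence is loosely worded and the highest CTCAE grade was meant. A shift table needs categories, and the paragraph opens with CTCAE grading. On that reading nothing is masked, and the separate table list may already be right. This is possible, but the text says value, and the same paragraph lists worst severity grade as a separate output. Shells based on worst grade would contradict the SAP as written, so the sentence needs correcting on either reading.

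The second reply is that other outputs carry the information, and much of this stands. Worst grade, by-visit values and changes, time to event and time to resolution are all planned. SAP 3 defines treatment-emergent events to include worsening, Protocol 14 treats worsening of a pre-existing laboratory abnormality as an adverse event, and Protocol 14.1 requires every Grade 4 result to be recorded as one. SAP 6.4.1 summarizes Grade 3 and 4 events separately. For neutrophils and platelets the worst-grade summary supplies nearly everything the shift table would. None of these outputs, however, cross-classifies each subject's baseline grade against the worst grade, and adverse event recording below Grade 4 depends partly on the investigator's judgment.

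It is also fair to say that the size in subjects is unknown and that the examples use assumed values. No hypothesis test or stopping rule in the documents uses these tables.

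**Conclusion.** The concern holds: the shift rule is wrong as written. Followed literally, it loses the low direction for 10 of 17 collected and graded tests. For 8 of those 10, entry limits do not let the worst-grade summary separate new from pre-existing abnormality. Leukopenia, one of the two toxicities named from the prior trial, is among the 8.

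The consequence is minor to moderate. It is confined to descriptive shift tables, the falls remain visible elsewhere in the safety analysis, and efficacy is unaffected. The conclusion rests on reading the sentence literally and applying it to every test, because the text makes no exception and the shells are not part of the SAP. No proportion of affected subjects is claimed. The correction should be made.

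**What to change.** Replace the shift-table sentence in SAP 6.4.2 with wording such as: *Shift tables will be provided from baseline CTCAE grade to the worst post-baseline CTCAE grade, using the lowest value for low-direction parameters, the highest value for high-direction parameters, and separate tables for each direction where CTCAE grades both.*

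Check the separate table list and shells against this sentence so that all three agree. The cut-offs are already in SAP Table 10.2.1. The cost is one sentence and a shell edit, plus the extra tables for the seven tests graded in both directions. No new data are needed.

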6.4.3 Physical Examination

The physical exam data will be listed by treatment arm at the screening visit, at post RFA on Day 0, Day 7 for subjects with elevated bilirubin, Day 14, Day 28, Month 5, Month 9, Month 13 or disease progression, whichever occurs first.

6.4.4 Vital Signs

Vital signs, (temperature (in Celsius), blood pressure, pulse rate, and respiration) will be collected at the screening visit, Day 0: pre-dose assessment the morning of the RFA procedure, post-RFA within 15 minutes after completion of study drug infusion, within 30 minutes and 1 hour after RFA procedure, then every 2 hours until the subject is stable or discharged, Day 7 for subjects with elevated bilirubin, Day 14, Day 28, Month 5, Month 9, Month 13 or disease progression, whichever occurs first.

Vital signs will be summarized at each visit by treatment arm for actual values and change from baseline. The last on-study value will also be presented (called 'End of Study'), with change from baseline.

6.4.5 12-Lead ECGs

12-Lead ECGs will be acquired at screening, post Day 0: post RFA, Day 28, Month 5, Month 9, and Month 13 or disease progression, whichever occurs first.

For all 12-lead ECG abnormal findings will be presented for the actual values and change from baseline by visit and treatment arm.

Frequency tables will be provided by visit for QTcB and QTcF for the following categories:

- QTc <= 450 ms
- 450 ms < QTc <= 480 ms

- $480 \text{ ms} < \text{QTc} \leq 500 \text{ ms}$
- $\text{QTc} > 500 \text{ ms}$

Frequency tables will be provided by visit for the changes from baseline of QTcB and QTcF for the following categories:

- QTc change from baseline $\leq 30 \text{ ms}$
- $30 \text{ ms} < \text{QTc change from baseline} \leq 60 \text{ ms}$
- QTc change from baseline $> 60 \text{ ms}$

6.4.6 Echocardiograms/MUGA scans for LVEF monitoring

A baseline echocardiogram (ECHO) will be carried out at the screening visit. Measurements with a MUGA scan are allowed if an echocardiogram cannot be performed; however, the same modality used at baseline must be used on Day 28 and at Month 13 or at time progression of disease, whichever occurs first.

Counts and percentages of abnormal echocardiograms/MUGA scan will be summarized for each treatment arm at each visit.

LVEF monitoring will be assessed at screening, Day 0: post RFA, Day 28, Month 5, Month 9, and Month 13 or disease progression, whichever occurs first.

LVEF % will be summarized by treatment arm at each visit for actual values and change from baseline.

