10. SCHEDULE OF STUDY PROCEDURES

Table 1: Schedule of Study Evaluations

Protocol Section	Procedure/Test	Screening / Baseline	Treatment Period ¹							Follow-Up Period			
			Procedure Day			Post-Procedure Visits (+/- 3 days)				Safety and Efficacy Assessments			
		-21 Days	Pre-Dose	Time 0	RFA + 15 min.	Post RFA	Day 7 ²	Day 14	Day 28	M5, M9, M13 or Progression ³	M17, M21, M25	6 Month Interval after M25	3 Month Interval after Progression
Evaluation and Observations													
17.1	Informed Consent	X ⁴											
10.1.3	Demographics and Medical History	X											
10.1.5	Physical exam	X				X	X	X	X				
10.1.6	Vital Signs	X ⁵	X ⁵			X ⁵	X	X	X	X			
10.1.7	ECOG Performance	X											
14	Adverse Event Eval.	X	→	→	→	→	→	→	X ⁶	X ⁶			
11	Con. Med. Update	X	→	→	→	→	→	→	X				
Treatment Procedures													
8.1	IRT System/ Randomization	X ⁷											
8.2	Pre-Medication Regimen		X ⁸										
8.2	IV Study Drug Infusion			X ⁹									
8.3-8.4	RFA Procedure				X ¹⁰								

Protocol Section	Procedure/Test	Screening / Baseline	Treatment Period ¹							Follow-Up Period			
			Procedure Day				Post-Procedure Visits (+/- 3 days)			Safety and Efficacy Assessments			
		-21 Days	Pre-Dose	Time 0	RFA + 15 min.	Post RFA	Day 7 ²	Day 14	Day 28	M5, M9, M13 or Progression ³	M17, M21, M25	6 Month Interval after M25	3 Month Interval after Progression
Safety Procedures/Lab Tests													
10.1.10	LVEF Monitoring	X ¹¹							X ¹¹	X ¹¹			
10.1.9	12-Lead ECG	X				X			X	X			
10.1.11	Serum pregnancy test	X											
10.1.12	CBC with differential	X					X	X	X	X			
10.1.12	Serum chemistry ¹²	X					X	X	X	X	X		
10.1.12	PT/INR	X					X	X	X	X	X		
10.1.12	Urinalysis	X					X	X	X	X			
Disease Assessment													
10.1.4	Biopsy		X ¹³										
10.1.8	Imaging ¹⁴	X							X	X	X	X	
15.2.1	Overall Survival ¹⁵												X ¹⁵

- Retreatment** – Subjects are eligible for one retreatment no later than 21 days after the Day 28 imaging scan. The retreatment must be the same (sRFA + dummy or sRFA + ThermoDox) as initially administered.
- Day 7 Visit** – Only subjects with a total bilirubin > 2.0 but \leq 3.0 mg/dL must undergo the additional safety visit on Day 7 post-RFA.
- Time of Progression** – Month 13 visit assessments are required at time of disease progression, whichever occurs first within the first 13 months. No further assessments required after progression is recorded

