- Informed Consent** – Is required within 28 days prior to study drug infusion. Informed Consent should be obtained prior to any study-related procedure performed outside standard medical care and required only to evaluate for participation in this trial.

5. **Vital Signs** – Assess screening vital signs prior to randomization and perform a *pre-dose assessment the morning of the RFA procedure*. Post-RFA vital signs should be assessed within 15 minutes after completion of study drug infusion, within 30 minutes and 1 hour (+/- 15 min.) after RFA procedure, then every 2 hours (+/- 15 minutes) until the subject is stable or discharged.
6. **Adverse Event Evaluation** – Assess adverse events (AEs) through Day 28 following study drug treatment. AEs after Day 28 evaluated as possibly, probably or definitely related to the study drug or the RFA procedure will be recorded at any point during the trial and are to be followed until resolution or the patient is clinically stable.
7. **Randomization** – Eligibility criteria must be assessed prior to randomization. *Randomization must occur at least 24 hours prior to scheduled RFA treatment time* to ensure that the oral pre-medication regimen can be started.
8. **Pre-Medication Regimen** - A blinded oral pre-medication capsule is dispensed after randomization with instructions to take the pre-medication 24 hours (+/- 2 hours) prior to the scheduled RFA procedure time. Recommend a reminder phone call be made to the subject the morning prior to RFA treatment. IV premedication (active or dummy infusion) is administered within 30 mins. (+15 min.) prior to study drug infusion.
9. **IV Study Drug Infusion** – Infusion is intended to be 30 minutes in duration; however, the complete contents of the infusion bag must be infused.
10. **RFA Procedure** – 15 minutes (+5 min) after the start of study drug infusion, RFA is to be initiated and is to be completed within 3 hours of the start of study drug infusion. **RFA procedure should achieve an RFA dwell time of ≥ 45 minutes.**
11. **LVEF Monitoring** – LVEF monitoring is required at baseline, at Day 28, and at Month 13 or radiologic progression, whichever occurs first. Echocardiogram is preferred. MUGA scans are permitted if an echo cannot be completed; however, the same method of measurement must be used to evaluate LVEF in an individual subject.

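### SAP 6.4.6 lists LVEF visits that the protocol does not schedule, and plans no any-time per-subject count of LVEF decline with a size threshold

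*SAP*

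**What the plan says.** **Planned LVEF output (SAP 6.4.6).** There are two summaries, both by visit. One is continuous: "LVEF % will be summarized by treatment arm at each visit for actual values and change from baseline". The other is categorical: "Counts and percentages of abnormal echocardiograms/MUGA scan will be summarized for each treatment arm at each visit". The SAP gives no definition of abnormal.

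**Visits in the SAP.** The same section says "LVEF monitoring will be assessed at screening, Day 0: post RFA, Day 28, Month 5, Month 9, and Month 13 or disease progression". Its own first paragraph differs: the baseline modality "must be used on Day 28 and at Month 13 or at time progression of disease". SAP 1.2 and SAP 5 also give Month 13 or progression as the only late LVEF assessment.

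**Visits in the protocol.** Table 1, footnote 11: "LVEF monitoring is required at baseline, at Day 28, and at Month 13 or radiologic progression, whichever occurs first". Section 10.1.10 agrees. Footnote 3 adds that "Month 13 visit assessments are required at time of disease progression, whichever occurs first within the first 13 months".

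**A decline criterion in the protocol.** Section 10.1.10 describes a fall of more than 10% in resting LVEF to an abnormal value, explained there as below the institution's lower limit of normal. Its only use is to prompt a repeat examination once cumulative doxorubicin reaches 300 mg/m². The SAP does not cite it.

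**Other safety measures in the SAP.** Laboratory data get worst grade and baseline shift tables (6.4.2). For QTc (6.4.5), "Frequency tables will be provided by visit for the changes from baseline of QTcB and QTcF for the following categories".

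**The concern.** Comparing safety between the arms is a secondary objective, and protocol 6.2.4 names cumulative-dose cardiotoxicity as one of doxorubicin's two primary toxicities. LVEF is the direct measurement of it.

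Two things look wrong. First, the visit list in SAP 6.4.6 does not match the scans that will exist. A programmer who follows it would produce rows with no data, or rows defined by disease progression. Second, cardiac decline is typically a matter of a few subjects with large falls. By-visit means dilute such falls. By-visit abnormal counts do not say how many different subjects were affected over the trial, or by how much.

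What is at stake is the clarity of one safety table. No efficacy result depends on it.

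**Working it through.** **1. Visit lists side by side**

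| Post-baseline point | SAP 6.4.6 list | Protocol (footnote 11, 10.1.10) |
|---|---|---|
| Day 0 post-RFA | yes | no |
| Day 28 | yes | yes |
| Month 5 | yes | only if progression occurs then |
| Month 9 | yes | only if progression occurs then |
| Month 13 or progression | yes | yes |

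Five points against two: 5 − 2 = 3 that the protocol does not schedule as such. The list matches the ECG schedule in SAP 6.4.5 ("12-Lead ECGs will be acquired at screening, post Day 0: post RFA, Day 28, Month 5, Month 9, and Month 13 or disease progression"), which suggests that it was carried over.

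Table 1 does mark LVEF in a column shared by Months 5, 9, 13 and progression, but footnote 11 on that mark limits it to Month 13 or progression. So if scans are filed by nominal visit, the Month 5 and Month 9 rows hold only subjects who progressed then, and the Month 13 row loses them. If they are filed as progression scans, the Month 5 and Month 9 rows are empty. Neither version is a useful by-visit summary.

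**2. What a by-visit mean can show**

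Shift in arm mean = (proportion affected) × (points lost). Assume 275 per arm (550 ÷ 2), and suppose that 1% to 5% of an arm lose 10 to 20 points:
- 1% (275 × 0.01 ≈ 3 subjects) losing 10 points: 0.01 × 10 = 0.1 point
- 5% (275 × 0.05 ≈ 14 subjects) losing 20 points: 0.05 × 20 = 1.0 point

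A mean change of 0.1 to 1.0 point would hardly be noticed.

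**3. What an abnormal count can show (illustration)**

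The documents give only the entry limit, LVEF ≥ 50%. Assumed: baseline normal with mean 62 and SD 5, truncated at 50; limit of normal 50; SD of change 6 or 8; two post-baseline scans with changes correlated 0.5; no drug effect; 275 subjects.

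| Expected subjects per arm, scatter alone | SD 6 | SD 8 |
|---|---|---|
| Below 50 at one scan | 15.9 | 27.0 |
| of these, fall of 10 points or less | 9.0 (57%) | 9.3 (34%) |
| Ever below 50 over two scans | 25.6 | 42.8 |
| Worst value below 50 with fall > 10 points (5–95% range) | 12.3 (7–18) | 29.9 (22–39) |
| Same, reading >10% as relative | 22.6 | 40.4 |

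With baseline mean 60 the small-fall share is 64% or 43%; with mean 65 it is 44% or 22%. Adding the size threshold removes 1 − 12.3/25.6 = 52% or 1 − 29.9/42.8 = 30% of the subjects ever below 50.

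The threshold does not make the count sharp. If five subjects truly fall by 20 points at the later scan, the expected count rises only to 16.2 (11–22) or 33.4 (25–42), and the ranges overlap those with no true falls. The reading of >10% also has to be stated, because it changes the count materially.

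**4. Why the protocol's repeat-scan rule does not fill the gap**

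300 ÷ 50 = 6 full doses are needed to reach the trigger. The Month 13 or progression scan follows at most the initial treatment and one retreatment, 2 × 50 = 100 mg/m². The further repeat treatments, up to five, come only after the PFS event.

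**The case against.** **The abnormal count already captures decline.** This largely stands. Protocol 10.1.10 explains abnormal LVEF as below the institutional lower limit, and that is the best reading of the SAP term too. Eligible subjects enter at 50% or more, so with a limit of 50% every later abnormal value is a fall from baseline to below normal. A reader might infer that the plan cannot detect falls to below normal, or that the term has no meaning; the documents support neither. What is missing is an any-time count and a size threshold. The argument weakens where an institution's limit is above 50%, since a subject could then be abnormal at entry.

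**Three visits with no scan is too strong.** This stands for Months 5 and 9, where progression scans can fall. Only Day 0 post-RFA can never have a protocol scan. The correct schedule also appears elsewhere in the SAP, and SAP 1.3 defers to protocol section 10.

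**Adverse event tables count affected subjects.** In part. Protocol section 14 makes an abnormal diagnostic result an adverse event if it leads to treatment, further evaluation or significant clinical signs, and SAP 6.4.1 tabulates incidence by arm. But a confirmatory repeat of the same test does not qualify, and a repeat examination is all that 10.1.10 asks for. After Day 28 only related events are recorded.

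**The comparison with other measures proves little.** Fair: the QTc categories are also by visit, and the table list is a separate document that may contain more.

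**The new count hardly separates zero from five true cases.** True under the assumptions above. It is descriptive only.

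**Conclusion.** The point holds in two limited parts. The visit list in SAP 6.4.6 is an error against the protocol and against the SAP's own text. It would lead to empty rows or rows selected on progression; the scans actually taken do not change. Second, within the SAP and protocol text, no per-subject, any-time count of LVEF decline with a size threshold is planned, and the existing tables cover it only in part.

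A reader might go further and infer that cardiac safety is not being monitored, or that a signal would be missed. The documents do not support that: scans are scheduled, values and changes are summarised, abnormal scans are counted and individual data are listed. Protocol 6.2.4 ties the cardiac risk to cumulative dose (1 to 2% cardiomyopathy at 300 mg/m²) and reports that 84.8% of the prior trial's active arm had a single 50 mg/m² dose.

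Severity is minor, with no effect on overall survival, alpha or power. The visit comparison rests on the text alone. The LVEF counts rest on assumed baseline, scatter and correlation and only illustrate the point.

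**What to change.** In SAP 6.4.6:

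1. List LVEF at baseline, Day 28 and one combined Month 13 or progression row. State where scans taken for or after retreatment are shown; retreated subjects have the higher cumulative dose.
2. Define abnormal by reference to protocol 10.1.10, as LVEF below the institutional lower limit of normal.
3. Add a descriptive n (%) per arm of As-Treated subjects, among those with a baseline and at least one post-baseline LVEF, whose worst post-baseline value (retreatment scans included) fell by more than 10 percentage points to below the institutional lower limit, or below 50% if that limit is not recorded. Apply it at any cumulative dose. State that percentage points is a chosen reading of the protocol's >10%, and that the count is to be read against the control arm.

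Keep the by-visit summaries. The cost is some SAP wording and one table from values already collected. The downside is that scatter alone will partly fill that table.
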